8 STATISTICAL CONSIDERATIONS

8.1 Study Endpoints

8.1.1 Primary Endpoints

Primary Objective: Evaluate severe acute respiratory syndrome coronavirus 2 (SARS-CoV-2) transmission following exposure in Kindergarten through 12th grade schools.

Primary Endpoints:

- Proportion and number of students with positive COVID-19 test following known within-school exposure.
- Proportion and number of staff with positive COVID-19 tests following known within-school exposure.
- Proportion and number of exposures undergoing the test-to-stay protocol that result in additional (tertiary) transmission.
- Time to test positivity among those exposed to SARS-CoV-2 and undergoing the test-to-stay protocol.

8.1.2 Secondary Endpoints

Secondary Objective #1: Characterize the effect of individual-level masking on SARS-CoV-2 spread.

Secondary #1 Endpoints:

- Proportion and number of masked students with positive COVID-19 test who were exposed to SARS-CoV-2 from masked versus unmasked individuals.
- Proportion and number of masked staff with positive COVID-19 test who were exposed to SARS-CoV-2 from masked compared to unmasked individuals
- Proportion and number of unmasked students with positive COVID-19 tests who were exposed to SARS-CoV-2 from masked compared to unmasked individuals
- Proportion and number of unmasked staff with positive COVID-19 tests who were exposed to SARS-CoV-2 from masked compared to unmasked individuals

Secondary Objective #2: Characterize the effect of exposure setting on SARS-CoV-2 spread.

Secondary #2 Endpoints:

- Proportion and number of students with positive COVID-19 test after indoor vs. outdoor exposure.
- Proportion and number of students with positive COVID-19 test after athletic vs. classroom exposure.
- Proportion and number of students with positive COVID-19 test after bus vs. classroom exposure.

Secondary Objective #3: Describe COVID-19-related school absences for up to 14 days following within-school SARS-CoV-2 exposure.

Secondary #3 Endpoints:

- Total number of school days missed due to symptoms after exposure.
- Total number of school days missed due to isolation after positive COVID-19 test.
- Total number of school days missed due to quarantine after SARS-CoV-2 exposure.

8.2 Analysis Plan

Summary statistics of the schools and the students/staff will be presented using data collected during study enrollment. Means/medians with standard deviations (and interquartile ranges) will be tabulated.

8.2.1 Primary Analysis

For the primary endpoint the proportion of students/staff with positive COVID-19 test will be reported and the trend by week will be presented in graphical form. To account for the within-school correlation of outcomes, 95% confidence intervals will be estimated for the proportion using a generalized estimating equations approach using a working independence correlation structure.¹²

8.2.2 Secondary Analysis

The proportion and number of students/staff who reported masking and unmasking will be reported and presented in graphical form. The primary analysis will be repeated for masked and unmasked participants (students and staff) separately. The primary analysis will be repeated for masked and unmasked source of exposure separately.

School absences will be analyzed by absences due to symptoms, positive COVID-19 test, or due to quarantine for exposure to SARS-CoV-2. To account for the within-school correlation of outcomes, analyses will be conducted using a generalized estimating equations approach using a loglink suitable for count outcomes, with a working independence correlation structure.

To account for within-school correlation, a risk between the schools using a generalized estimating equation approach with an identity link and a working independence correlation structure will be estimated. The risk difference will be estimated for each semester during the study period, as well as overall. Students will be censored by end of data or study withdrawal. Censoring will be addressed by incorporating inverse-probability censoring weights into the regression model, with censoring risk estimated with a Kaplan-Meier estimator.

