Yet, current policies and procedures requiring quarantine after close contact exposures to limit further spread have led to hundreds of thousands of missed school days and have threatened the school workforce, greatly impeding school operations and the ability of children to appropriately learn. In the fourth quarter of 2021 in NC alone, more than 40,000 students and staff were required to quarantine as a result of being a close contact of a COVID-19 case (unpublished). Fortunately, recent CDC and local guidance have eliminated quarantines for most exposed, unvaccinated, asymptomatic children who are wearing a mask and who are in close contact with another masked, infected child within the classroom setting. However, many quarantines continue to result in unvaccinated adults, children exposed to infected adults, and masked exposures occurring outside of the classroom (e.g., athletics or busing). Moreover, schools and local governments are steadily lifting mask mandates, even as local community cases rise, contributing to exponential increases in quarantines that not only keep children and staff out of schools and parents out of work, but have often overwhelmed school resources and the public health system.

To address the issue of quarantines while ensuring that the school and surrounding community remain safe from SARS-CoV-2 spread, some locales have begun implementing a "test to stay strategy", whereby a close contact undergoes serial testing over a specified duration of time.

The close contact must wear a mask during this time period but is not required to undergo quarantine as long as the screening tests remain negative and the contact remains asymptomatic. While this strategy is supported by strong scientific premise and initial data are promising, the impact of this strategy on quarantine, and secondary and tertiary within-school transmission has not been systematically evaluated.

This study will partner with schools to allow students and staff to remain in school following exposure if they continue to test negative for COVID-19 over pre-determined intervals. This study aims to collect data to assess the spread of SARS-CoV-2 in school communities with varying mitigation strategies to provide data-backed guidelines for mitigation strategies in schools. The study team will work with NCDHHS and a safety monitoring team on a weekly basis to interpret data, evaluate safety, and design next steps (e.g. testing frequency and timing).

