1.6 Secondary Analysis

- Objective: The proportion of students/staff who reported masking and unmasking will be summarized and presented in a bar chart to see the trend by testing day.
 - The primary analysis will be repeated for masked and unmasked participants (students and staff) separately.
 - The primary analysis will be repeated for masked and unmasked source of exposure separately.
- Objective: School absences will be analyzed by absences due to symptoms, positive COVID-19 test, or due to quarantine for exposure to SARS-CoV-2.
 - To account for the within-school correlation of outcomes, analyses will be conducted using a generalized estimating equations approach using a loglink suitable for count outcomes, with a working independence correlation structure (Zeger et al. 1988).

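### Neither document plans an estimate or interval for the masking and setting differences that secondary objectives 1 and 2 ask about

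*Protocol*

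**What the plan says.** - **Objectives.** Protocol 8.1.2 words secondary objective 1 as "Characterize the effect of individual-level masking on SARS-CoV-2 spread", and objective 2 in the same form for exposure setting. SAP 1.1 keeps both as aims.
- **Comparisons listed.** Under objective 1 there are four, one for each combination of student or staff and masked or unmasked participant. The first is "Proportion and number of masked students with positive COVID-19 test who were exposed to SARS-CoV-2 from masked versus unmasked individuals". Under objective 2 there are three, all in students, starting with "Proportion and number of students with positive COVID-19 test after indoor vs. outdoor exposure" and followed by athletic against classroom and bus against classroom.
- **Masking analysis.** Protocol 8.2.2 and SAP 1.6 repeat the primary analysis by participant masking and then by source masking; in the SAP, "The primary analysis will be repeated for masked and unmasked source of exposure separately". The primary analysis (protocol 8.2.1, SAP 1.5) is a proportion with a 95% CI from a working-independence GEE.
- **Between-group estimate.** Protocol 8.2.2 says that "a risk between the schools using a generalized estimating equation approach with an identity link and a working independence correlation structure will be estimated", and then: "The risk difference will be estimated for each semester during the study period, as well as overall". It adds: "Censoring will be addressed by incorporating inverse-probability censoring weights into the regression model". SAP 1.5 and 1.6 contain neither the risk difference nor the weights.

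**The concern.** An objective that asks for the effect of something needs an estimate of a difference or ratio, with its uncertainty. This plan delivers proportions for separate subsets and leaves the comparison to the reader. That matters because protocol 1.1.1 gives the purpose as "to provide data-backed guidelines for mitigation strategies in schools". Someone writing guidance on masks, buses or athletics wants to know how far apart two risks are and how well that gap is known. Two of the three secondary objectives would be reported without that figure, and for setting without any stated analysis.

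**Working it through.** **Step 1: set the listed contrasts against the planned analyses.**

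| Contrast (protocol 8.1.2) | Listed in SAP 1.3? | Planned proportions | Planned difference with CI |
|---|---|---|---|
| Masked vs unmasked source, in masked students, masked staff, unmasked students, unmasked staff (4) | No; Secondary #1 repeats the four primary endpoints | By participant masking and by source masking; the text does not say the two splits are crossed | None |
| Indoor vs outdoor, students | Yes | None stated | None |
| Athletic vs classroom, students | Yes | None stated | None |
| Bus vs classroom, students | Yes | None stated | None |

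Manuscripts 2 and 3 do not fill the gap. SAP 2.6 and 3.6 give intervals for single attack rates. SAP 2.8 handles setting by leaving out athletic and outside-school exposures, not by contrasting them with others. The count of planned intervals is 0 for a masking difference and 0 for a setting difference.

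**Step 2: does the protocol's risk difference cover them?** It is described as between schools, with no grouping factor, outcome or population. The seven contrasts are between exposed individuals, classified by data collected at enrollment (protocol 5.3). A comparison of schools is a different question, so carrying that sentence into the SAP would not have supplied the contrasts.

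**Step 3: do separate 95% CIs stand in for an interval on the difference?** The documents give no sample size, event rate or effect size, so there is no figure of the plan's own to reproduce. In general:

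- SE_d = sqrt(SE1² + SE2² − 2·rho·SE1·SE2), where rho is the correlation between the two estimates.
- Two intervals fail to overlap when |difference| > 1.96·(SE1 + SE2).
- With SE1 = SE2 and rho = 0, that threshold is 1.96 × 2/√2 = 2.772 standard errors of the difference. Two-sided error = 2·(1 − Phi(2.772)) = 0.0056, not 0.05.
- A difference detectable with 80% power lies at 1.960 + 0.842 = 2.802 standard errors. Power by non-overlap = Phi(2.802 − 2.772) = Phi(0.030) = 0.51.

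**Step 4: an illustration on assumed figures.** Take 3% vs 5% positive with 1,000 per group and no clustering. Then SE1 = sqrt(0.03 × 0.97/1000) = 0.00539, SE2 = sqrt(0.05 × 0.95/1000) = 0.00689 and SE_d = 0.00875. The separate CIs, 1.94–4.06% and 3.65–6.35%, overlap. The CI for the difference, 2.00 ± 1.96 × 0.875, runs from 0.28 to 3.72 points and excludes zero. Power is 63% from the difference and 32% from non-overlap.

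**Step 5: shared schools.** Assume 2% vs 4%, 1,200 per group and design effect 2. Then SE1 = sqrt(2 × 0.02 × 0.98/1200) = 0.00572 and SE2 = sqrt(2 × 0.04 × 0.96/1200) = 0.00800. The separate CIs are 0.88–3.12% and 2.43–5.57% whatever rho is. The CI for the difference is not fixed:

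| rho | 95% CI for the difference (points) |
|---|---|
| −0.3 | −0.18 to 4.18 |
| 0 | 0.07 to 3.93 |
| +0.3 | 0.37 to 3.63 |
| +0.5 | 0.60 to 3.40 |

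The same pair of published intervals is compatible with all four rows. Only a model for the difference, clustered on school, shows which applies.

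**The case against.** The strongest defence is that this is a descriptive study. Its objectives say characterize and describe, protocol 8.3 makes no sample size calculation, no hypothesis test is planned, and exploratory subgroup work is allowed. All of that stands. It rules out calling this a failed or underpowered test, and gives no ground for demanding a lead contrast or a testing hierarchy. It does not excuse the gap: an estimation study still needs an estimate of what its objective names.

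A second defence is that the between-school risk difference may have a sensible meaning. Protocol 1.1.1 speaks of communities with differing mitigation, and protocol 3.1 collects school-level practices. This also stands, and it is a reason to let the sponsor define the comparison instead of simply deleting it.

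Four stronger readings are tempting but unsupported:

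- A reader might infer that the GEE sentence specifies a degenerate model, with school as both the compared factor and the cluster. The documents never specify that model; the sentence is incomplete.
- A reader might infer that the SAP's omission of the risk difference is what cost the masking and setting contrasts. Step 2 shows that it is a separate gap.
- A reader might see inflated false-positive risk across seven contrasts. That needs each difference to be tested at 5%, and the documents plan neither tests nor difference intervals.
- A reader might quote one fixed loss of precision from separate intervals. That depends on whether masking varies within or between schools. SAP 2.2 and 3.2 describe optionally and universally masked districts, so some of the variation may lie between schools.

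Finally, a clustered interval does not turn an unadjusted difference into a causal effect. That is true, and limits what the remedy achieves.

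**Conclusion.** The concern holds as a gap in specification. None of the seven contrasts listed under secondary objectives 1 and 2 has a planned difference or interval. Setting is worse off than masking because it has no stated analysis at all. SAP 1.3 has in addition lost the four masking endpoints. Protocol 8.2.2's between-school risk difference is undefined, is missing from the SAP, and would not close the gap.

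The general size is the 0.0056 error and the fall from 80% to about 51% power, both for equal, independent standard errors. The figures in steps 4 and 5 rest on assumed rates, group sizes, design effect and correlations, and show direction only. The primary endpoints are not affected. This is a cheap improvement that should be made.

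**What to change.** 1. In protocol 8.2.2 and SAP 1.6, for each pair listed in protocol 8.1.2 (masked vs unmasked source within each of the four participant groups; indoor vs outdoor; athletic vs classroom; bus vs classroom), fit a group indicator in the identity-link, working-independence GEE clustered on school. Report the risk difference with its 95% CI beside the two separate proportions.
2. In SAP 1.3, replace the repeated primary endpoints under Secondary #1 with the protocol's masking endpoints.
3. For the between-school risk difference, state the groups of schools, the outcome and the use of the censoring weights, and carry it into the SAP; or withdraw it from protocol 8.2.2.
4. Present the differences as unadjusted estimates, not tests.

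The cost is a wording amendment and one extra model per contrast, seven in all. The model form is already in the protocol, and participant masking, source masking and place of exposure are already collected. With a single two-level indicator, the fitted difference equals the difference of the two raw proportions, so the planned proportions do not change. Where a group has very few positives or few schools, the robust interval will be unreliable, and the report should say so.

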3.2 Study Definition of Enrollment

Study enrollment is defined as the participant has provided informed consent (or assent) and completed at least one day of testing in an effort to avoid quarantine.

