3.3 Study Definition of Completion

An individual will complete the study after completing all testing days and symptom monitoring (up to 14 days), or data entry that explains why all testing was not completed (e.g., positive test, symptoms, quarantine).

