1.5 Primary Analysis

- Objective: The proportion of students/staff with positive COVID-19 test following known within-school exposure and the proportion of exposures undergoing the test-to-stay protocol that result in additional transmission will be summarized overall, by student or staff, by school district, by school level.
 - To account for the within-school correlation of outcomes, 95% CI will be estimated for the proportion using a generalized estimating equations approach using a working independence correlation structure (Zeger et al. 1988).
 - Objective: Days to test positivity among those exposed to SARS-CoV-2 and undergoing the test-to-stay protocol will be summarized by median and interquartile ranges and nonparametric estimate of test positivity probability will be plotted.

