3.2 Data

TTS data collected from K-12 students and staff with household exposures within 4 districts and 1 charter school in North Carolina (NC) employing universal masking.

- Establish population cutoff
 - [name] (Statistical programmer): Here are the number of household exposures with test results on or after days 5, 7, and 9: \geq Day 5 = 282; \geq Day 7 = 251; \geq Day 9 = 214
 - [name] (Project leader): Given that ~65% of population made it into analysis eligible population for day 9, we will use this day as the cutoff, which is consistent with CDC guidance for household close contacts

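### SAP Manuscript #1 has no rule for participants who stop testing early; as written they most plausibly stay in the denominator as non-positive, which biases the primary positivity proportions low

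*Protocol*

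**What the plan says.** **Enrolment and schedule.** Under protocol 3.2 a person is enrolled once consent is given and they have "completed at least one day of testing in an effort to avoid quarantine". Protocol 5.4 schedules tests on Days 1, 3, 5 and 7, and allows the number and timing of tests to change later.

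**Primary proportions.** Protocol 8.2.1: "For the primary endpoint the proportion of students/staff with positive COVID-19 test will be reported". SAP 1.5 takes this up for Manuscript #1: "The proportion of students/staff with positive COVID-19 test following known within-school exposure" is summarised with an interval from generalized estimating equations. SAP 1.2 uses the enrolled population for all analyses and applies no exclusions to reach the analysis-eligible population. SAP 1.4 assigns the scheduled day when a test date is missing and says nothing about a test that was not done.

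**Time to positivity.** SAP 1.5 plots a nonparametric estimate and gives no censoring time.

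**Censoring.** The protocol's only rule is in 8.2.2: "Students will be censored by end of data or study withdrawal". It continues: "Censoring will be addressed by incorporating inverse-probability censoring weights into the regression model, with censoring risk estimated with a Kaplan-Meier estimator". Both sentences belong to the paragraph on a between-school comparison, where "The risk difference will be estimated for each semester during the study period, as well as overall". Neither the risk difference nor the weighting appears in the SAP.

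**Other manuscripts.** Manuscripts #2 and #3 (SAP 2.3, 3.3) define an analysis-eligible set: people who tested positive, or who had a late negative (Day 5 or Day 9 onward) and completed follow-up.

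**The concern.** Positivity can be observed only up to a person's last test. Someone who is negative on Day 1 and skips the rest has been observed for one test out of four, yet meets the enrolment definition and belongs to the Manuscript #1 analysis set. A crude proportion over that set gives this person the same weight as someone with four negatives. Infections that the missed tests would have found are left out of the numerator while the person stays in the denominator.

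Three things are at stake.

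- The student and staff proportions, which are primary endpoints meant to inform quarantine policy, would understate transmission.
- The repeats by masking of the participant and of the source (SAP 1.6) would be distorted if test completion differs between those groups.
- The time-to-positivity curve may censor the same people at their last test. Its end point and the crude proportion would then disagree about one quantity.

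Protocol 13.6 tracks deviations only indirectly, through missing data, so no other planned report would show how many tests were missed.

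**Working it through.** **1. The plan's own figures.** The documents give no test-completion rate for Manuscript #1. The nearest counts are in SAP 3.2 and 3.3 (household exposures): 335 records, 322 enrolled, 265 analysis eligible. SAP 3.2 adds, "Here are the number of household exposures with test results on or after days 5, 7, and 9": 282, 251 and 214.

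- 335 − 13 = 322, as stated.
- 214/322 = 66.5% and 214/335 = 63.9%; both fit the plan's figure of about 65%.

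**2. How many never-positive people stopped before Day 7.** Assume that the base is 322 and that everyone with a Day 9 or later result is eligible.

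- No result on or after Day 7: 322 − 251 = 71.
- Eligible without a Day 9 or later result, hence positive: 265 − 214 = 51.
- Lower bound: if all 51 were positive before Day 7, 71 − 51 = 20 stopped (20/322 = 6.2%).
- Upper bound: those not eligible number 322 − 265 = 57 (17.7%). This is reached only if all 251 − 214 = 37 people whose last result fell on Days 7–8 were positive; then 51 − 37 = 14 were positive earlier, and 71 − 14 = 57.

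**3. Effect on a crude proportion.** Crude/true = Σ (share of positives at each test × completion at that test). Assume shares of 20/30/30/20% over the four tests and a linear fall in completion.

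- To 94% (100, 98, 96, 94): 0.200 + 0.294 + 0.288 + 0.188 = 0.970, or 3% too low.
- To 82% (100, 94, 88, 82): 0.200 + 0.282 + 0.264 + 0.164 = 0.910, or 9% too low.

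**4. Comparison of three estimators.** Assume a true 7-day risk of R = 5%, spread evenly over four tests, and non-informative stopping with probability d after each negative test.

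- Stoppers kept as non-positive: C = R × [1 + (1−d) + (1−d)² + (1−d)³]/4.
- Positive or Day 7 negative only: C / [C + (1−R)(1−d)³].
- Kaplan-Meier censored at the last test.

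| d | Stoppers kept | Positive or late negative | Censored at last test |
|---|---|---|---|
| 5% | 4.64% (−7%) | 5.39% (+8%) | 5.00% |
| 10% | 4.30% (−14%) | 5.84% (+17%) | 5.00% |
| 20% | 3.69% (−26%) | 7.05% (+41%) | 5.00% |

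The share of never-positive people who reach the last test is (1−d)³ = 86%, 73% and 51%. Only the first row lies within the 82–94% used in step 3; the others show how the bias grows. The eligible-set rule of Manuscripts #2 and #3 does not repair the problem, because it keeps every positive but drops incomplete negatives, and so errs upward.

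**The case against.** The strongest reply is that no sentence in either document says a person who stops testing counts as negative through Day 7. The SAP's general principles take non-missing values as the denominator and leave open whether an incomplete test series is missing. If incomplete negatives were dropped, the bias would be upward. This stands as far as it goes: the downward direction is the most natural reading of SAP 1.2 and 1.5, not a stated rule. But one negative result is itself a non-missing value, SAP 1.2 excludes nobody, and under the other reading the denominator is still undefined.

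Four stronger readings are tempting and are not supported.

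- A reader might infer that the SAP removed a safeguard from the primary endpoints. It did not: the 8.2.2 rule was written for a secondary risk difference. Nor is it certain that the rule ignores the last test, since the end of data is undefined.
- A reader might infer that the plan handles incomplete follow-up nowhere else. Manuscripts #2 and #3 do, with eligible sets, exclusion of missing data and rates in both populations. Manuscript #3 also describes an imputation range, marked as left out of the manuscript. They cover other populations, however.
- A reader might infer that silent stoppers count as completers under protocol 3.3. That needs a "data entry that explains why all testing was not completed (e.g., positive test, symptoms, quarantine"), and no Manuscript #1 analysis uses completer status.
- A reader might take 71/322 = 22% as the stopping rate. That counts early positives as stoppers and exceeds the cap of 57.

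It is also fair to say that the endpoint as worded is an observed proportion, so a cumulative risk is partly a choice of estimand. That is a reason to report both.

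**Conclusion.** The point holds for Manuscript #1 and should be fixed. Neither document defines the outcome, denominator or censoring time of a participant who stops testing before the schedule ends. On the most plausible reading, student and staff positivity is biased low, and the masking comparisons can be distorted if completion differs between groups.

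The size is illustrative: about 3–9% too low in relative terms if 6–18% of those enrolled stop without a positive result. That rests on household data with a Day 9 cutoff carried over to within-school exposures, on the base of 322 and the eligibility assumption in the working, and on an assumed timing of positives and a linear fall in completion. The exact recovery of 5.00% by censoring at the last test also assumes that stopping is unrelated to infection.

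**What to change.** In SAP 1.5, end each participant's at-risk time at the last valid test, for students and staff alike. Report cumulative positivity to the end of the test schedule in force (Day 7 in the initial phase) with that censoring. Use inverse-probability-of-censoring weights built on variables already collected, such as school level, semester and daily symptoms, and a school-clustered interval. Weights with covariates are preferable to an unadjusted Kaplan-Meier censoring model because stopping may depend on symptoms or school.

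Show this beside the crude proportion and a table of completion by test day. Use the same censoring for the time-to-positivity curve, so that curve and proportion can be reconciled. If the risk difference in protocol 8.2.2 is kept, change its censoring time to the last completed test.

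The cost is wording in both documents and modest programming, with no new data. Reported positivity becomes slightly higher.
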